### 2.3.3. Analysis of Secondary Outcome

Secondary outcomes, including inquiring about the buyer's age, requesting ID

cards for age verification, and dissuading buyers from use, will be analyzed in a similar manner to the primary outcome. Chi-square tests will be used to detect the statistical significance of differences between the two study groups, and logistic regression models, adjusted for covariates and appropriate for the distribution of the outcomes, will be employed. Additionally, similar national maps describing geographic variations will be generated.

#### **2.3.4. Analysis of Other Outcomes**

Other outcomes, including illegal flavored products, online contact, and delivery service offered, will be analyzed in a similar way as the primary outcome. Chi-square tests will be used to detect statistical significance in differences between the two groups, and logistic regression models appropriate for the distribution of the binary outcomes with covariate adjustments will be employed. Similar national maps describing geographic variations will be generated as well. For marketing claims and strategies, we will further employ thematic framework analysis to qualitatively analyze and describe the marketing methods and tactics of e-cigarette stores.

#### **2.3.5. Subgroup Analysis**

For matched e-cigarette and cigarette stores, we will employ McNemar's tests to assess the distinctions in the outcomes between e-cigarette stores and cigarette stores. Rates of successful e-cigarette purchases stratified by age checking behaviors and buyer attire will also be reported. Planned subgroup analyses are intended to explore potential effect modifications of gender, age, metropolitan area and store types.

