Eligible stores as study subjects will be identified from the AutoNavi Map through keyword searches. Stores are eligible for enrollment if they have reachable contact information and claim to be open for business on a regular basis when contacted. The expected number of stores sampled in each metropolitan area is approximately 32, if the number allows, for a minimum expected total enrolment of approximately 1080 sellers nationwide. In addition, we plan to conduct the same trial for cigarette stores and perform a 1:1 match with e-cigarette stores. This will allow us to compare sellers' behaviors between the two attire groups in both cigarette and e-cigarette stores.

The overall study design is described by a flow chart as follows (Figure 1):

[figure not shown]

Figure 1 Flow Chart of Study Design

4. Study subjects

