## 1.1. Overview

### 1.1.1. Study Design

This study is a two-armed, national-level, open-label cluster RCT conducted among e-cigarette stores located in 36 metropolitan areas across mainland China (including 4 municipalities directly under the Central Government, 27 provincial capitals, and 5 cities specially designated in the national plan). This RCT will adopt the mystery shopping approach to measure the effect of adolescent buyers' type of attire (school uniforms vs. casual attire) on the likelihood of sellers' compliance with the minimum age restriction for e-cigarette sales, defined by both age verification and sales. The e-cigarette stores will be randomly assigned to the intervention group or control group at a ratio of 1:1. Each store in the intervention group will receive a simulated buyer dressed in a school uniform, while each store in the control group will receive a simulated buyer dressed in casual attire. The simulated buyers in this study are adolescents aged 18-19 years old. The simulated buyers will attempt to purchase e-cigarette products and record the behaviors and marketing claims of the sellers, as well as store internal and external characteristics.

Eligible stores as study subjects will be identified from the AutoNavi Map through keyword searches. Stores are eligible for enrollment if they have reachable contact information and claim to be open for business on a regular basis when contacted. The expected number of e-cigarette stores sampled in each metropolitan area is approximately 32, with an additional 8 e-cigarette stores serving as backups, if the

number allows, for a minimum expected total enrollment of approximately 1,080 retailers. In addition, we plan to conduct the same trial for cigarette stores and perform a 1:1 match of e-cigarette stores and cigarette stores, allowing us to compare the business practices of e-cigarette stores and cigarette stores between the two attire groups.

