### **1.2.2. Secondary Objectives**

- To determine the impact of type of attire by adolescents on in-store communication between sellers and customers, specifically dissuading use.
- To discern the differences in regulation compliance-related behaviors between e-cigarette and cigarette retailers.

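### The matched-store analysis tests product only: the between-attire comparison the cigarette visits are said to allow has no clearly specified analysis, and pairs sharing a buyer-day are treated as independent

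*SAP*

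**What the plan says.** SAP 1.1.1 describes the 1:1 match as "allowing us to compare the business practices of e-cigarette stores and cigarette stores between the two attire groups". Protocol section 3 (Study Design) is more explicit: "This will allow us to compare sellers' behaviors between the two attire groups in both cigarette and e-cigarette stores".

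The analysis is in SAP 2.3.5, with the same wording in Protocol 8.5: "For matched e-cigarette and cigarette stores, we will employ McNemar's tests" to "assess the distinctions in the outcomes between e-cigarette stores and cigarette stores". No attire term, attire stratum or allowance for clusters is mentioned. Two other sentences there bear on the point. One is descriptive and limited to e-cigarettes: "Rates of successful e-cigarette purchases stratified by age checking behaviors and buyer attire will also be reported". The other says subgroup analyses are meant to "explore potential effect modifications of gender, age, metropolitan area and store types", with no model and no definition of the last item.

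The listed secondary objective (SAP 1.2.2, Protocol 2.3) does not mention attire: "To discern the differences in regulation compliance-related behaviors between e-cigarette and cigarette retailers".

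On structure, SAP 1.1.2 assigns each geographic cluster to one buyer and sets attire by day. Protocol 7.6 has the same buyer visit a nearby cigarette store after each e-cigarette store. SAP 1.4 gives cluster size 4, an intracluster correlation of 0.5 and about 1,080 e-cigarette stores, hence about 1,080 pairs.

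**The concern.** There are two separate faults.

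First, purpose and analysis do not match. A paired test of product uses only pairs whose two stores behaved differently, and it has no place for attire. It cannot say whether a uniform changes seller behaviour in cigarette stores, or whether the gap between the two products depends on what the buyer wears. The attire contrast in cigarette stores is also the one that inherits the random allocation, because the buyer arrives in the attire set for that day. The product contrast is not randomised. So the comparison with the stronger design behind it is the one without a clearly specified analysis.

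Second, McNemar's test assumes independent pairs. Here about four consecutive pairs share a buyer, a day, an attire and a neighbourhood. If the product difference varies from one buyer-day to another, the p-value is too small.

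**Working it through.** **Step 1. Questions against named analyses.**

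| Question | Raised in | Analysis named |
|---|---|---|
| Overall product difference | SAP 1.2.2, Protocol 2.3 | McNemar, SAP 2.3.5 |
| Attire effect in e-cigarette stores | SAP 1.2.1 | Chi-square and logistic, SAP 2.3.2 to 2.3.3 |
| Attire effect in cigarette stores | Protocol 3 | None clearly specified |
| Product difference by attire | SAP 1.1.1 | None clearly specified |

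**Step 2. What a pooled test estimates.** The plan gives no size or power for the matched comparison, so there is no figure to reproduce. Purchase rates are left to the pilot, so every rate below is assumed.

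McNemar's statistic is (b − c)²/(b + c), with b and c the two discordant counts. Pooled over 1:1 arms, b − c tracks ½(D_uniform + D_casual), where D is the e-cigarette minus cigarette sale rate. With e-cigarette sales of 60% (uniform) and 90% (casual), and cigarette sales of 75% in both arms, this is ½(−15 + 15) = 0 points.

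Rejection rates at 5%, from 20,000 runs of 1,080/2 = 540 independent pairs per arm:

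| Assumed rates, e-cigarette vs cigarette | Pooled McNemar | McNemar within arm | Between-arm contrast of paired differences |
|---|---|---|---|
| Uniform 0.40 vs 0.50; casual 0.60 vs 0.50 | 4.9% | about 91% each | 99.6% |
| Uniform 0.40 vs 0.50; casual 0.50 vs 0.50 | 64% | 91%; 5% | 64% |
| Uniform 0.45 vs 0.50; casual 0.45 vs 0.60 | 99.6% | 38%; 99.8% | 65% |

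Check of the first row:
- Discordance per arm is 0.4×0.5 + 0.6×0.5 = 0.50.
- Variance per arm is (0.50 − 0.10²)/540 = 0.000907.
- SE of the contrast is √(2×0.000907) = 0.0426, so z = 0.20/0.0426 = 4.70.
- If the paired difference had an intracluster correlation as high as 0.5, the design effect would be 1 + 3×0.5 = 2.5. Then z = 4.70/√2.5 = 2.97, and power is Φ(2.97 − 1.96), about 84%.

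Cancellation occurs only in the first row. With same-sign differences (third row) the pooled test rejects readily, but it says nothing about whether the arms differ.

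**Step 3. Clustering.** The relevant correlation is ρ_D, that of the within-pair difference, not of the outcome. If both stores of a pair have the same sale probability given the cluster, the expected difference is zero in every cluster and ρ_D = 0. Simulated with 270 clusters of 4 pairs (270×4 = 1,080): outcome correlation 0.50, ρ_D 0.00, McNemar size 5.1%.

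Otherwise the true size of a nominal 5% test is about 2[1 − Φ(1.96/√(1 + (m − 1)ρ_D))]. For m = 4 and ρ_D = 0.1: 1.96/√1.3 = 1.719, giving 8.6%.

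| ρ_D | 0 | 0.05 | 0.1 | 0.2 | 0.5 |
|---|---|---|---|---|---|
| m = 4 | 5.0% | 6.8% | 8.6% | 12.1% | 21.5% |
| m = 5 | 5.0% | 7.4% | 9.8% | 14.4% | 25.8% |

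Size 4 is in SAP 1.4. About 5 is in SAP 1.1.2, which divides all 40 selected stores, backups included, over 8 clusters.

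The documents give no ρ_D. Simulation with 270 clusters of 4 pairs and an assumed cluster-level product effect on the logit scale, for base rates of 50% to 90%, gave these McNemar sizes:
- no product variation: about 4% to 5%
- SD 0.5: about 6%
- SD 1.0: 6% to 8%
- SD 1.5: 9% to 12%

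The lower ends belong to the higher purchase rates. A cluster-robust paired test held about 5%.

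**The case against.** Much of the opposing case stands.

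- *The listed objective is met.* The secondary objective asks only for the product difference, and a paired test answers it on average. The between-attire comparison appears in design statements, not among the objectives or hypotheses. A reader might infer that the cigarette visits would answer nothing. The documents do not support that, since the visits also serve the descriptive aims in SAP 1.2.3.
- *The plan may already cover it.* *Store types* could mean e-cigarette versus cigarette: SAP 2.2.2 calls mall or street the store's location, which leaves the term free. Against this, item 8 of the assessing tool (Protocol Appendix 4) uses store type for the mall, street, convenience or office-building format. Both documents also speak of running the same trial in cigarette stores, which might carry over the chi-square and logistic analyses. But SAP 2.2.1 defines the primary outcome for e-cigarettes, and SAP 2.3.1 refers to e-cigarette seller behaviour. So the analysis is not clearly specified, rather than ruled out.
- *Pooling is inferred.* The SAP writes of tests in the plural and does not say pooled. Pooling is the natural reading where no stratum is named.
- *Clustering is a separate matter.* It is not why the attire comparison is missing.

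Two stronger inferences also fail. The pooled test need not hide differences by arm: full masking requires opposite signs and similar size. And the stated correlation of 0.5, with its design effect of 2.5, should not be applied directly to McNemar's test, because a cluster effect shared equally by both stores of a pair cancels.

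**Conclusion.** The point holds in this form: the attire comparison involving cigarette stores, which both documents say the matched design allows, has no clearly specified analysis, and the one named test ignores the correlation between pairs. This is worth correcting but does not touch the primary analysis of attire in e-cigarette stores.

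The cost of leaving out attire depends on unknown rates. It runs from complete cancellation (4.9% rejection against about 91% within each arm, under assumed opposite 10-point differences) to simple averaging when the differences share a sign. The type I error of McNemar's test is near nominal if cluster effects are shared within pairs, and about 6% to 12% at assumed logit SDs of 0.5 to 1.5. The inflation is therefore conditional and often modest. These figures rest on assumed rates, 540 pairs per arm and clusters of 4.

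**What to change.** In SAP 2.3.5, with the same change in Protocol 8.5:

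1. Analyse both store types together with a logistic GEE or mixed model containing product, attire and product × attire. Cluster-robust analysis of paired differences, contrasted between arms, is an acceptable alternative.
2. Cluster the variance on the randomised cluster (buyer-day). Add a sensitivity analysis clustering on buyer, because the planned 25 buyers (Protocol 7.3) recur across cities. With so few buyers a small-sample correction is advisable.
3. Report the product difference within each attire arm, the attire effect within each store type, and the interaction, each with a confidence interval.
4. Define *store types*.
5. Keep McNemar's test, if wanted, as a descriptive supplement.

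The cost is a few lines of SAP text, which SAP section 1 says is finalised before database lock, and one more model. No extra visits or data items are needed.

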### **3. Software Documentation**

All the statistical analyses will be conducted using Stata MP 17 (StataCorp, College Station, TX, US). The maps depicting geographic variations will be generated using DrawChinaMap (<https://rdrr.io/github/psychbruce/drawMap/src/R/drawChinaMap.R>).

